8	of treatment with mitoquinone/mitoquinol mesylate (mito-MES) (20 mg daily) daily to prevent
9	any viral infection in high-risk close contacts of cases with possible viral infection.
10	
11	
10	Diagnosis and Kay Subject Selection Criteria (Evolusion and Inclusion).
12	Diagnosis and Key Subject Selection Criteria (Exclusion and inclusion):
13	
14	Inclusion criteria
15	All enrolled participants must meet the following criteria:
16	1. Age 18-65 years old. Rationale: We will recruit 18-65 years old participants to increase
17	feasibility of the study and to ensure the study results are generalizable. Participants older
18	than 65 years old have higher incidence of many comorbidities including kidney, heart and
19	liver disease. It would be important to first document safety in the setting of viral infection in
20	the absence of established kidney, liver and heart disease and other major morbidity.
21	2. Asymptomatic (no symptoms of viral infection) on study entry.
22	3. Exposure to a person with at least two new onset independent symptoms or signs (fever) of
23	respiratory viral disease. Viral infection will be defined clinically based on history obtained by
24	the investigator who is an infectious diseases physician and stringent criteria will be

followed. Viral infection will be defined as presence of at least two new onset independent
symptoms or signs (fever) of respiratory disease that cannot be attributed to bacterial cause.
For example, the combination of coryza (runny nose) and sore throat is very characteristic of
a viral illness since there is no bacterial "rhinitis". The combination of fever and cough is not
specific enough presentation since it can be attributed also to bacterial bronchitis or
pneumonia. A study participant with chronic allergies or chronic sinusitis or asthma will not
be included in the study since they may have chronic runny nose or headache or cough.

8 4. High risk exposure without use of masks to suspected case of viral infection (based

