9 on history and the study definition in the household within 5 days prior to study entry. Highrisk exposure was defined as prolonged (>24 hour) and intimate (< 6 feet) exposure to index 10 case without personal protective equipment (e.g., face mask) in poorly ventilated indoor 11 12 areas. To increase chances that differences in treatment efficacy between the compared 13 groups will be shown will as small sample size as possible, the study team enrolled participants with particularly high risk exposure to the index case defined as: a) direct care 14 for the index case; b) had close direct physical contact with the index case; c) lived with the 15 index case; d) had close indoor contact (within 6 feet), with or without direct physical 16 17 contact, for at least 24 hours; e) had direct contact with infectious body fluids, including oral secretions, respiratory secretions, or stool. For example, we included several parents that 18 were exposed to infected children (who also infected their siblings) and included an 19 extended window of recurrent and continuous high-risk exposure to independent confirmed 20 21 SARS-CoV-2 infections within the household. In these particularly high-risk exposures, there was direct contact with children during childcare and while the children were symptomatic 22 (fever, cough, coryza, fatigue); 23

5. With at least 4 COVID-19 diagnostic tests in case of negative test results. To minimize
 false negative tests, we included participants who had multiple independent SARS-CoV-2
 diagnostic tests with sensitivity >90% per test;

Adequate renal function determined by the Cockcroft-Gault formula for creatinine clearance
 (>60 mL/min/1.73 m2

3 7. Able and willing to communicate in English

4 8. Able and willing to provide informed consent to take part in the study

5 9. Able and willing to provide medical/surgical history

6 10. Availability to have follow up for all study visits, barring unforeseen circumstances

- 7
- 8

In addition, for the *mito-MES group*, the following inclusion criteria were applied:

9

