12		contraception. Rationale: Since the study drug (mito-MES) has not been studied in pregnant
13		women, women and men of child bearing potential should use a barrier method that
14		prevents pregnancy in combination with a highly effective method of contraception. Highly
15		effective methods are:
16		oral contraceptive
17		
 
Use of condoms during any sexual intercourse during the study period
 

18		intrauterine device
19		intrauterine hormonal releasing systems
20		Bilateral tubal ligation/occlusion
21		• Vasectomized partner provided that partner is the sole sexual partner of the participant and
22		that the vasectomized partner has received medical assessment confirming surgical
23		success.
24		
25	Giv	ven how essential it is to start potential treatment as soon as possible after high-risk exposure
26	to	a viral infection, participants will be allowed to participate without waiting for the results of a

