1 diagnostic test such as SARS-CoV-2 FDA approved test (can delay initiation of treatment for at 2 least 24-48 hours). If a participant has a positive SARS-CoV-2 during the study, then the participant will be allowed to continue the study only if not eligible for another FDA approved 3 treatment for COVID-19, given the potential favorable antiviral and anti-inflammatory effects of 4 5 mito-MES in SARS-CoV-2 infection. However, these participants with a positive SARS-CoV-2 6 test will not be included in the final analysis of this PEP trial. The data obtained from the participants with a positive SARS-CoV-2 test will set the foundation for future studies of use of 7 8 mito-MES as treatment for acute COVID-19. 9 Exclusion criteria for all study participants: 10 11 Participants who meet any of the following criteria at screening will be excluded from the study: 12 1. Use of Coenzyme Q10 or Vitamin E < 120 days from enrollment 13 2. Women with variations in physiological functions due to hormones that may effect immune 14 function and (transgender, **pregnant**, breastfeeding) 3. Pregnant (based on history) or lactating. If the possible study participant is female and 15 sexually active and there is a possibility based on history (timing of most recent sexual 16 17 intercourse and timing of menstrual period) that the possible study participant is pregnant, then the participant will be excluded from the study. Rationale: Additional pregnancy testing 18 will further delay the initiation of treatment and will further compromise feasibility of the study 19

20 given limited resources.

Absence of significant clinical disease clinical diseases [e.g., cardiovascular disease (such as coronary artery/vascular disease, stroke), heart disease (such as congestive heart failure, cardiomyopathy, atrial fibrillation), lung disease (such as chronic obstructive pulmonary disease, asthma, bronchiectasis, pulmonary fibrosis, pleural effusions), kidney disease (glomerular filtration rate or GFR less than 60 ml/min/1.73 m2), liver disease (such as

cirrhosis, hepatitis), cancer, major immunosuppression (such as history of transplantation,

1		HIV infection)] based on history. Rationale: Significant clinical diseases can confound
2		interpretation of results for safety and efficacy (e.g., symptomatic viral infection). For
3		example, a patient with known major lung disease such as chronic obstructive pulmonary

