1 The following secondary outcomes are based on **either non guantitative** criteria (categorical) 2 or criteria that may not be available for all the study participants (for example FDA approved diagnostic tests). The study will not pay for any diagnostic tests. These diagnostic tests for 3 viruses may be available in the setting of real world setting and clinical care of each participant 4 5 (for example if performed by the participant or ordered by a doctor in the setting of clinical care). 6 Development of new onset fever (T> 100.3 F or 38C) based on documented 7 8 measurements of temperature on a daily basis throughout the duration of the study. 9 Temperature will be recorded in a diary and recording temperature would be a requirement 10 for study participation. 11 **Duration** of ANY of at least three respiratory/systemic symptom of viral illness in **days** (Symptom 1: fever, Symptom 2: cough, Symptom 3: coryza, Symptom 4: sore throat, 12 Symptom 5: shortness of breath, Symptom 6: chills, Symptom 7: fatigue, Symptom 8: loss 13 of smell or taste, Symptom 9: myalgias, Symptom 10: arthralgias, Symptom 11: headache, 14 Symptom 12: nausea, Symptom 13: vomiting, Symptom 14: diarrhea 15 Confirmation of viral infection based on a FDA approved diagnostic test (for example 16 17 respiratory panel PCR that also detects RSV and influenza or other respiratory viruses, rapid antigen test for SARS-CoV-2, PCR for SARS-CoV-2). 18 Symptomatic viral infection: proportion of participants with fever, cough, or other 19 20 respiratory/systemic symptoms (including but not limited to fatigue, loss of smell or taste, 21 myalgias, arthralgias, shortness of breath, sore throat, headache, chills, coryza, nausea, 22 vomiting, diarrhea). 23 Symptomatic moderate to severe viral infection. Based on established score system a viral illness will be categorized as moderate or severe if the participant grades at least 2 different 24 25 symptoms as "moderate" or "severe".

- Symptomatic PCR confirmed SARS-CoV-2 infection
- 2 Need for oxygen therapy (days)
- Hospitalization: Days of hospitalization attributable to viral disease: The median number of
   days (or partial days) spent admitted to an acute care hospital
- Respiratory failure requiring ventilatory support attributable to viral disease: The median
   number of days (or partial days) requiring (i) non-invasive or (ii) invasive ventilation

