### 1 Sessions by study staff

2 There are a total of 5 study visits over a period of 14 days. Day 0 is the day of exposure to

3 SARS-CoV-2.

4 Session 1 (before D0): Screening and enrollment. A medical history, study questionnaire,

5 eligibility assessment, informed consent will be performed by the investigator

6 Session 2 (before D0 or days 0-4): Dispension (allocation) of mito-MES (the study team will

7 ship overnight the compound to the study participants).

8 **Session 3 (day 1):** Telephone consult. Medication use, history (review of systems), adverse

9 event assessment, adherence diary, symptom diary, temperature diary will be assessed.

10 **Session 4 (day 7):** Telephone consult. Medication use, history (review of systems), adverse

11 event assessment, adherence diary, symptom diary, temperature diary will be assessed.

12 Session 5 (day 14): Telephone consult. Medication use, history (review of systems), adverse

13 event assessment, adherence diary, symptom diary, temperature diary will be assessed.

1	
2	Sessions by study participant
3	
4	Sessions by study participant
5	Day 1-21: Performance of diagnostic SARS-CoV-2 test in nasal swab
6	
7	Daily on D1-14
8	Adherence diary
9	Symptom diary
10	Temperature diary
11	
12	Symptom severity scores will be recorded on days 0, 1, 7, 14 by history.
13	All study visits will be remote (phone call or video visit).
14	
15	Screening
16	The following parameters will be reviewed:
17	HIV status
18	• Age
19	• Gender
20	Underlying condition and comorbidities
21	Medications
22	Pregnancy status (if applicable)
23	• Demographic characteristics: Birth sex, gender, race, ethnicity (sex will be considered as
24	a biological variable);

•	Behavioral risk factors:	Cigarette smoking	(yes or no, pack years	s), alcohol use;
---	--------------------------	-------------------	------------------------	------------------

 Clinical factors: Body-mass index (BMI), hypertension (based on self-report and medications), diabetes (based on self-report and medications), kidney disease (self-report),
 liver disease (self-report and medications), adjudicated myocardial infarction (MI)(self-report and medications), and hepatitis C virus (self-report and medications), use of hormones (e.g. testosterone or contraceptives)(self-report and medications), menopausal status (selfreport);

8

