## 5 Interpretation of Results/Statistical Analyses:

6

There is no formal hypothesis testing in this exploratory study and a comparison with a 7 8 dedicated control group. Observational and descriptive data related to efficacy and safety of use 9 of MitoQ for viral infections will be obtained and these data will set the foundation for larger 10 controlled clinical trials. All categorical and continuous data (outlined above) will be recorded as 11 median and interguartile range (given small sample size). Exploratory analyses will be 12 conducted by parametric or non-parametric tests for continuous or categorical parameters as appropriate to explore whether the primary outcomes defer between men and women. The 13 14 severity of symptoms will be compared first by categorical analysis (symptoms present yes or 15 no) via Fisher's exact Chi square, and subsequently via the independent two-sample t test for symptom severity among those who are symptomatic. Non-normally distributed data will be 16 17 analyzed via the Mann–Whitney U test. Females may have differences in mitochondria 18 compared to males of identical age. We will conduct secondary analyses to explore if effects of 19 MitoQ will vary by sex and race; however, a fully powered, sex- and race-stratified analysis is beyond the scope of this study. 20

21

Sensitivity analyses: Sensitivity analyses will be performed based on established guidelines
 regarding the performance of sensitivity analyses in clinical trials. Intention-to-treat analysis
 (as primary analysis), As-treated analysis, Per-protocol analysis will be performed to assess
 non-compliance or protocol violation. Analyses will be performed with and without outliers as

assessed by z-score or boxplot. The primary analysis will be compared with the analysis that
ignores clustering with one primary method chosen to account for clustering. Analysis will be
performed with and without adjustment for baseline characteristics. Finally, analyses will be
performed under different distributional assumptions, if applicable.

5

Adjustments for multiple comparisons: Notably, the proposed study is exploratory and there is
 less need for a multiple-testing correction, as any false-positive findings will not change practice.
 Any findings will be tested in further confirmatory clinical trials.

9

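### Inclusion criterion 5 (at least four COVID-19 tests if negative) makes study membership depend on results after entry, and conflicts with intention-to-treat and with the separate exclusion of positives

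*Combined protocol and SAP*

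**What the plan says.** All references are to the combined protocol and SAP.

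- **The rule.** The general inclusion list opens with "All enrolled participants must meet the following criteria". Item 5 is "With at least 4 COVID-19 diagnostic tests in case of negative test results". Its stated purpose is to limit false negatives by using several independent "diagnostic tests with sensitivity >90% per test". Nothing comparable is asked of a person who tests positive.
- **Timing.** The paragraph that closes the inclusion criteria says "participants will be allowed to participate without waiting for the results of a" diagnostic test. The Participant timeline table marks one swab before entry or on days 0 to 4, then daily swabs to day 21. The list of participant sessions repeats this: "Day 1-21: Performance of diagnostic SARS-CoV-2 test in nasal swab".
- **Availability.** The introduction to the secondary efficacy measures says "The study will not pay for any diagnostic tests" and that test-based endpoints may be lacking for some participants.
- **Positives.** The paragraph that closes the inclusion criteria also says that participants with a positive SARS-CoV-2 "test will not be included in the final analysis of this PEP trial".
- **Analysis set.** Under Sensitivity analyses, intention-to-treat is listed first, followed by "as primary analysis), As-treated analysis, Per-protocol analysis will be performed to assess" non-compliance or protocol violation.
- **Outcomes.** The primary efficacy outcomes are clinical: any symptom of viral infection within 14 days, and a symptom severity score. Test-confirmed infection is secondary.

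**The concern.** An inclusion criterion should be decidable when a person joins. This one is not: whether someone satisfies it depends on later test results and, for negatives only, on how many tests were taken. One positive test is enough, while a negative person needs four. If some negatives fall short and the criterion is applied as worded, people leave the denominator because of their result and their testing behaviour. That is selection on an outcome, and it cannot be squared with an intention-to-treat primary analysis.

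The study has no formal hypothesis test. Under Power/Sample Size, its stated product is an effect size to inform larger randomised trials, so a rate computed on a result-selected denominator would carry into those designs.

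**Working it through.** **No figure to reproduce.** The plan states 80 enrolled, based on resources. It gives no infection rate and no share of negatives expected to reach four tests. The values of p and q below are therefore assumptions.

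**1. The aim of the rule.** With per-test sensitivity of 0.90 and independent tests, the chance of missing an infection is 1 − 0.9 = 0.1 after one test and 0.1^4 = 0.0001 after four. The aim is sound arithmetically, but this has no bearing on who is counted.

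**2. Criterion 5 alone, confirmed SARS-CoV-2 rate.** Let p be the true rate and q the share of negatives who reach four tests, with all positives kept and tests accurate. The reported rate is p / (p + (1 − p)q).

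| True rate p | q = 1 | q = 0.9 | q = 0.7 | q = 0.5 |
|---|---|---|---|---|
| 10% | 10.0% | 11.0% | 13.7% | 18.2% |
| 20% | 20.0% | 21.7% | 26.3% | 33.3% |
| 30% | 30.0% | 32.3% | 38.0% | 46.2% |

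For example, p = 0.2 and q = 0.9 give 0.2 / (0.2 + 0.8 × 0.9) = 0.2 / 0.92 = 21.7%; q = 0.5 gives 0.2 / 0.6 = 33.3%. Because q cannot exceed 1, the reported rate cannot fall below p.

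**3. With the exclusion of positives as well.** The numerator becomes zero, so the confirmed SARS-CoV-2 rate in the final analysis is 0% for any p and q.

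**4. Primary symptom outcome.** Assume 30% infected, with symptoms in 70% of the infected and 20% of the uninfected. The true symptom rate is 0.3 × 0.7 + 0.7 × 0.2 = 0.21 + 0.14 = 35.0%.

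- Criterion 5 alone, q = 0.7 for all negatives: (0.21 + 0.14 × 0.7) / (0.30 + 0.70 × 0.7) = 0.308 / 0.790 = 39.0%.
- Criterion 5 alone, q = 0.9 for symptomatic and 0.6 for symptom-free negatives: (0.21 + 0.126) / (0.30 + 0.126 + 0.336) = 0.336 / 0.762 = 44.1%.
- Positives also excluded, q = 0.7 for all negatives: 0.098 / 0.490 = 20.0%.
- Positives also excluded, q = 0.9 and 0.6: 0.126 / (0.126 + 0.336) = 0.126 / 0.462 = 27.3%.

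On the same inputs, the symptom rate lies above 35.0% under one rule and below it under both.

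**The case against.** Four tests is a low bar against a schedule of daily swabs from day 1 to day 21. If participants follow it, q is close to 1 and criterion 5 removes almost no one. This stands as far as it goes. The documents say only that tests may be unavailable, so they do not establish a large shortfall. They do not exclude one either, since the tests are unpaid.

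The outcome that the rule touches directly is secondary, and the study is purely exploratory. Both statements are correct and limit the weight of the point. They do not make a result-dependent condition suitable as an entry criterion.

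One could read the four tests as preceding entry. That does not fit enrolment without waiting for a result, or a schedule in which nearly all swabs follow entry.

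A reader might infer three stronger claims that the documents do not support:

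- **That infection and illness rates are biased upward overall.** This holds for the confirmed rate only under criterion 5 in isolation. The exclusion of positives pulls the other way.
- **That participants have in fact been removed after follow-up.** No section says so, and nothing shows whether the 80 enrolled are counted before or after criterion 5 was applied.
- **That a treated-versus-untreated comparison is biased.** Unequal testing could do this: at a true 30% in both groups, q of 0.9 and 0.5 give 32.3% and 46.2%, a ratio of 0.70, and swapping q gives 1.43. But the wording on a control group is unclear. Criterion 4 mentions compared groups, while the statistical section appears to disclaim a dedicated control. No testing frequency by group is given.

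**Conclusion.** The point holds in a limited form. Criterion 5 is a one-sided condition, mostly settled after entry, placed in a list that everyone must satisfy. It conflicts with the intention-to-treat primary analysis.

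Taken alone, it can only raise the confirmed SARS-CoV-2 rate or leave it unchanged. At a true 20%, the rise is 1.7 percentage points if 90% of negatives reach four tests and 13.3 points if 50% do. It is near zero if daily swabbing is followed. These shares are assumptions, and the calculation keeps all positives. The effect on the primary symptom and severity outcomes runs only through who stays in the denominator, and its size needs further assumptions about symptoms and testing.

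The net direction for the plan as a whole is not determined, because the exclusion of positives would set the confirmed SARS-CoV-2 rate to 0%. The two rules have to be reconciled with each other and with intention-to-treat before any rate from this study can be interpreted.

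**What to change.** 1. Remove no. 5 from the inclusion criteria.
2. Define the primary intention-to-treat set by facts known at entry, whatever the later test results or number of tests, and use it for both primary outcomes.
3. Reconcile the analysis exclusion of SARS-CoV-2-positive participants with that set, so that a positive test during follow-up counts as an outcome. This concerns the analysis set only, not the rule on who continues treatment.
4. Keep the requirement of four or more tests if negative only as an evaluability or sensitivity condition for the SARS-CoV-2 secondary outcomes. Report the number not evaluable, and show the all-participant and evaluable-only rates side by side.

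The cost is a change of wording in two places and a few extra entries in one table. The all-participant rate will still contain some missed infections among people with few tests, which is why both rates should be shown. If people were already screened out under no. 5, their number should be reported and their data recovered where available. That would take more work than rewording.

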10 Viral infection will be defined clinically based on history obtained by the investigator who is an 11 infectious diseases physician and stringent criteria will be followed. Viral infection will be defined as presence of at least two new onset independent symptoms or signs (fever) of respiratory 12 disease that cannot be attributed to bacterial cause. For example, the combination of coryza 13 14 (runny nose) and sore throat is very characteristic of a viral illness since there is no bacterial 15 "rhinitis". The combination of fever and cough is not specific enough presentation since it can be attributed also to bacterial bronchitis or pneumonia. A study participant with chronic allergies or 16 17 chronic sinusitis or asthma will not be included in the study since they may have chronic runny 18 nose or headache or cough.

19

20 **Primary** measures of efficacy (will be assessed in ALL the study participants):

21

The following **primary** outcomes are based on criteria that can be obtained reliably and consistently for all the study participants (based on history and thermometer).

24

• Development of any symptom of viral infection within 14 days after exposure (YES/No).

1	• Severity of viral illness based on a quantitative score system. Each of the above 14
2	symptoms will be given a score based on severity: 1 for mild, 2 for moderate, 3 for severe.
3	Then a total severity score will be estimated (range of score is 0-42). Common example: a
4	person with mild coryza, sore throat and cough will be given a score of 3.
5	
6	
7	Secondary measures of efficacy (will be assessed in study participants but some endpoints
8	such as diagnostic tests may not be available in all the study participants):
9	
10	The following secondary outcomes are based on either non quantitative criteria (categorical)
11	or criteria that may not be available for all the study participants (for example FDA approved
12	diagnostic tests). The study will not pay for any diagnostic tests. These diagnostic tests for
13	viruses may be available in the setting of real world setting and clinical care of each participant
14	(for example if performed by the participant or ordered by a doctor in the setting of clinical care).
15	
16	
 
Development of new onset fever (T> 100.3 F or 38C) based on documented
 

17	measurements of temperature on a daily basis throughout the duration of the study.

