1. Initiation of Mito-MES within 5 days since exposure to index case. To ensure that a study 10 participant met this inclusion criterion, the study participant should have had high-risk close 11 12 contact with a confirmed COVID-19 case within the past 1-4 days prior to study entry. This 13 4-day window would also allow for up to 24-hour period for initiation of intervention (mito-MES) so that mito-MES would be started within 5 days since exposure to index case; 14 2. Successfully contacted by the study team within 24 h of study team notification of the 15 16 relevant index COVID-19 case. This time window is necessary because the efficacy of PEP 17 may be dependent on the timing of its initiation. Every effort was made by the study team to 18 include study participants who would be able to initiate mito-MES as soon as possible after notification of exposure to index case of SARS-CoV-2 infection. For many study participants, 19 Mito-MES was provided immediately after informed consent so that it would be available for 20 21 immediate use after anticipated exposure to confirmed case of SARS-CoV-2. It is well established that antivirals have highest efficacy when given as soon as possible (ideally 22 within 48 hours). This design with immediate initiation of Mito-MES within 72 hours post 23 24 exposure is different than the study design in a randomized controlled Phase 2/3 EPIC-PEP 25 (Evaluation of Protease Inhibition for COVID-19 in Post-Exposure Prophylaxis) of paxlovid given within 5 days post exposure from SARS-CoV-2 that failed to demonstrate therapeutic 26

1		efficacy (unpublished data). Time of initiation of the post-exposure prophylaxis (PEP)
2		treatment is critical in the setting of emerging SARS-CoV-2 variants that may establish
3		infection in less than 5 days.
4	3.	Ineligible for FDA approved alternative treatments to prevent progression to severe viral
5		infection including COVID-19 based on established criteria
6		https://www.cdc.gov/coronavirus/2019-ncov/need-extra-precautions/people-with-medical-
7		conditions.html. Rationale: If the study participant has confirmed exposure to SARS-CoV-2,
8		the participant will be allowed to enroll only if he/she is eligible for other FDA approved
9		treatments such as monoclonal antibodies or other antivirals for reasons such as personal
10		choice, allergies or lack of availability.
11	11	Willing to follow sexual abstinence during study period or highly effective method of

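### Illness is counted from exposure, but participants who enter later must still be symptom-free, so the reported 14-day illness rate is too low even if mito-MES does nothing

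*Combined protocol and SAP*

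**What the plan says.** Outcome window. The first primary measure of efficacy is "Development of any symptom of viral infection within 14 days after exposure (YES/No"). The clock starts at exposure, not at entry or first dose.

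Entry rules for everyone. Inclusion criterion 2 requires participants to be "Asymptomatic (no symptoms of viral infection) on study entry". Criterion 4 requires a high-risk household exposure no more than 5 days before entry.

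Extra rules for one group. The list that follows opens with "In addition, for the *mito-MES group*, the following inclusion criteria were applied", and its first item is "Initiation of Mito-MES within 5 days since exposure to index case". The explanation under that item places the contact 1 to 4 days before study entry and leaves up to 24 hours more to start the drug. Criterion 2 of the same list says that many participants received the drug straight after consent, ahead of an anticipated exposure. It also describes initiation within 72 hours, which has to be reconciled with the 5-day wording.

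Day 0. The schedule table under Participant timeline defines D0 as the day of study entry. Sessions by study staff defines it as the day of exposure, and dispenses drug at "Session 2 (before D0 or days 0-4): Dispension (allocation) of mito-MES (the study team will" ship it overnight).

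Analysis. Interpretation of Results/Statistical Analyses names intention-to-treat as primary and disclaims formal testing. It plans no landmark or delayed-entry analysis. Power/Sample Size reports 80 enrolled and promises an effect size for the design of larger randomized trials.

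**The concern.** A person exposed on Monday who falls ill on Wednesday, before being reached for consent, has an event inside the 14-day window but can never be enrolled. A person exposed the same day who is still well on Thursday can be. The enrolled group is therefore selected for having survived the first days symptom-free, while the outcome definition credits it with follow-up over those days. This is left truncation. It lowers the observed illness rate whatever the drug does, and a larger sample does not remove it.

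What is at stake is the effect size that Power/Sample Size promises to later trials. Set against a household attack rate counted from exposure, the treated rate would show a benefit from an inert drug, and trials designed on it would be too small.

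**Working it through.** The plan states no event rate, effect size or power, so it has no figure to reproduce. The check asks what an inert drug would show.

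**Inputs from the protocol**
- Outcome window: 14 days from exposure.
- Mito-MES entry: 1 to 4 days after exposure, with up to 24 hours more to first dose.
- Entry under the rules common to all: 0 to 5 days after exposure.

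**Assumptions (not in the protocol)**
- Risk r of ever falling ill: 30%, 50% or 70%.
- Time to symptoms: lognormal, median m of 3, 4 or 5 days, log-SD 0.5.
- Delays spread uniformly over each window.

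**Formulas**
- F(t) = Φ(ln(t/m)/0.5).
- True from-exposure rate = r·F(14).
- With F̄ the mean of F over the delay to the qualifying time, the observed rate = r·(F(14) − F̄)/(1 − r·F̄).

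**Worked case, r = 0.5, m = 3**
- F(14) = 0.999, so the true rate is 0.5 × 0.999 = 49.9%.
- Symptom-free at mito-MES entry: F̄ = 0.355. Rate = 0.5 × (0.999 − 0.355)/(1 − 0.5 × 0.355) = 39.1%.
- Symptom-free at first dose: F̄ = 0.473. Rate = 0.5 × (0.999 − 0.473)/(1 − 0.5 × 0.473) = 34.4%.
- Untreated, symptom-free at entry on days 0-5: F̄ = 0.371. Rate = 38.5%.

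| Risk, median | True rate | A: mito-MES, well at entry | B: mito-MES, well at first dose | C: common rule, days 0-5 | A/true | B/true | B/C |
|---|---|---|---|---|---|---|---|
| 30%, 3 d | 30.0% | 21.6% | 18.4% | 21.2% | 0.72 | 0.61 | 0.87 |
| 30%, 5 d | 29.4% | 27.0% | 25.5% | 26.1% | 0.92 | 0.87 | 0.98 |
| 50%, 3 d | 49.9% | 39.1% | 34.4% | 38.5% | 0.78 | 0.69 | 0.89 |
| 50%, 5 d | 49.0% | 46.0% | 44.1% | 44.9% | 0.94 | 0.90 | 0.98 |
| 70%, 3 d | 69.9% | 60.0% | 55.0% | 59.4% | 0.86 | 0.79 | 0.93 |
| 70%, 5 d | 68.6% | 65.9% | 64.2% | 64.9% | 0.96 | 0.94 | 0.99 |

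The rows for a 4-day median fall within the ranges of these four sets of ratios.

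**Splitting the sources**
- The asymptomatic-at-entry rule alone gives A/true of 0.72-0.96.
- The step from entry to first dose adds a further factor B/A of 0.85-0.97, but only if people who fall ill in that step are left out.
- If they are kept, mito-MES against the common rule (A/C) is 1.01-1.04. There is then no spurious benefit against untreated people enrolled under the common rule.

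**Sensitivity to delay.** If everyone qualifies on day 1, the ratio to the true rate is 0.99-1.00. If everyone qualifies on day 5, it is 0.21-0.75. A participant who consented and held drug before exposure loses no early follow-up, so the ratio is near 1.

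**The case against.** Four stronger readings are tempting, and the documents do not support them.

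1. A reader might infer that a consenter who falls ill before dosing is removed from the treated group. Only a literal reading of initiation as an inclusion criterion suggests this; no section says it. Retention limits study withdrawal to withdrawn consent and loss to follow-up, and intention-to-treat is primary. The explanation under the criterion works as a timing check at entry.

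2. A reader might infer that the symptom-free period is peculiar to the drug group. Most of it comes from criteria 2 and 4, which bind everyone, and the common entry window is no shorter than the mito-MES one.

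3. A reader might infer an apparent reduction of 38-82%. The formula does give that at 20-40% risk and a 3- or 5-day median, but only if everyone starts on day 5 and the comparator is counted from exposure. No section plans that comparison, and the wording on a control group is ambiguous. Many participants held drug before exposure.

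4. The remark that variants may establish "infection in less than 5 days" concerns infection, not symptom onset. It cannot show how much illness falls in the lost interval.

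It is also fair to say that the study is exploratory and has no formal test.

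These points limit the size and the urgency. They do not remove the mismatch between an outcome clock that starts at exposure and entry that comes later. Intention-to-treat cannot restore people who fell ill before they could enrol.

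**Conclusion.** The concern holds for the from-exposure illness rate. For participants who enter after exposure, that rate is biased downward whatever the drug does, and nothing in the plan corrects it. The direction follows from the entry rules; the size rests on the assumed risks, onset times and uniform delays.

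- Against the true from-exposure rate: about 0.61-0.94 if participants are symptom-free at first dose, or 0.72-0.96 if symptom-free at entry only.
- Against untreated people enrolled under the common 0-5 day rule: about 0.87-0.99, a spurious reduction of 1-13%. This arises only if consenters who fall ill before dosing are dropped, which the documents do not expressly say.
- For early starters and those holding drug before exposure: near 1.

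The documents do not give the mix of delays among the 80 enrolled, so the actual bias could be small. It should be corrected before any effect size is passed on. With no formal testing and an exploratory aim, it does not invalidate the study. The rule that leaves participants with a positive SARS-CoV-2 test out of the final analysis is a separate matter; it also lowers the observed rate and is not counted here.

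**What to change.** Because enrolment is complete, the changes belong in the analysis and the report.

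1. Reconcile the two Day 0 definitions. Count the primary outcomes over one fixed period from the later of exposure and study entry (consent). Counting from consent alone would fail for those who consented before exposure. Choose a period that the diaries cover for everyone. If diary days 1-14 run from exposure, a person entering on day 5 has 14 − 5 = 9 days; if they run from entry, 14.
2. Keep every eligible consenter with an exposure in the primary intention-to-treat set, whether or not drug was started. For that set, apply the initiation criterion as ability to start, judged at entry. Report how many fell ill before or without a first dose.
3. Tabulate illness by days from exposure to entry and from exposure to first dose, with those who held drug before exposure shown separately.
4. Restrict any untreated or published comparison, and the effect size promised under Power/Sample Size, to contacts still symptom-free at the same delay after exposure.

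Cost: clarified analysis definitions and additional tabulation. Exposure and entry dates are already needed for eligibility, and the adherence diary should give the first dose. The downside is that illness before the first dose counts against the drug, so the reported rate will be somewhat less favourable. The outcome period may also be shorter than 14 days.
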